#### **7.3.2 Laboratory Data**

Laboratory data will be summarized by treatment group as clinical relevance (normal/abnormal, without clinical relevance/ abnormal, with clinical relevance) and as continuous data (absolute values).

All laboratory data and changes from baseline will be described as continuous variables at each visit.

Treatment groups will be compared for the set of parameters (hematology set, biochemistry set, urinalysis set and microscopic urine examination set). Only clinically significant deviations (CS) will be taken into account. Permutation test will be used see 8 [2].

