3.3.4 Significant Potential Risks

Levopront® is a drug of Dompe Farmaceutici S.p.A., Italy, authorized in European Union and in extra European countries (Brazil, Mexico, Chile Columbia, Costa Rica, Ecuador, El Salvador, Guatemala, Honduras, Indonesia, Nicaragua, Panama, Philippines, Thailand, Venezuela, Turkey, South Korea), and established within the past two decades as a reliable and safe cough agent. Potential risks (known side effects) of Levopront® include:

Eye disorders: Mydriasis, bilateral blindness.

Immune system disorders: Allergic and anaphylactoid reactions, eyelid edema, angioneurotic edema, urticaria.

Psychiatric disorders: Nervousness, drowsiness, personality change, or personality disorder.

Nervous system disorders: Syncope, dizziness, vertigo, tremor, paraesthesia, tonic-clonic seizures and attacks of petit mal, hypoglycemic coma.

Cardiac disorders: Palpitations, tachycardia, atrial bigeminy.

Vascular disorders: Hypotension.

Respiratory, thoracic and mediastinal disorders: Dyspnea, cough, edema of the respiratory tract.

Gastrointestinal disorders: Gastric pain, abdominal pain, nausea, vomiting, diarrhea.

Hepatobiliary disorders: Cholestatic hepatitis.

Skin and subcutaneous tissue disorders: Urticaria, erythema, rash, pruritus, angioedema, skin reactions, aphthous stomatitis and glossitis. Epidermolysis.

Musculoskeletal and connective tissue disorders: Weakness of the lower limbs.

General disorders and conditions regarding the side of administration: General malaise, generalized edema, asthenia.

Preclinical study results have shown that the drug after acute and chronic dosing for 3 months has no toxic effects in warm-blooded laboratory animals (rodent and non-rodent species – rabbits), including developing organisms.

Potential risks of Libexin® include: hypersensitivity reactions: bronchospasm, skin rash, angioedema; GI tract disorders: dry mouth and throat, transient numbness and loss of sensitivity of the oral mucosa, stomach ache, predisposition to constipations, nausea; nervous system disorders: light sedative effect, fatigue (sedative effect and fatigue are observed at doses exceeding therapeutic, and all symptoms spontaneously resolve within several hours after drug discontinuation).

The study will include only the patients who agree to use adequate contraception measures for the whole study period.

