6.11 Tests Performed at Local Laboratory

Local laboratory will be used for laboratory tests. Collection, preparation and storage of biological samples will meet requirements of the study site local laboratory.

At baseline, all local laboratories will provide the required certificates and laboratory reference values. Local laboratory is responsible for sending laboratory reports to the Investigator, and for reporting abnormal laboratory values to the Investigator. Investigator should review the laboratory report, all abnormal values should be assessed, signed and dated. Deviations of laboratory values from baseline, reported as AEs should be appropriately reported in the source documentation and in CRF.

Patient randomization is performed before laboratory test results are available. In case of significant abnormality which, at the Investigator's opinion, could interfere with patient's participation in the study or impact interpretation of efficacy or safety parameters, the patient should be withdrawn from the study.

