**Table 9.28 Laboratory parameters. Biochemistry. Absolute values. Safety population. N = xx**

Similar

**Parameters to be presented:** Total protein, Albumin, Total cholesterol, Total bilirubin, Conjugated bilirubin, ALT, AST, Serum creatinine, Glomerular filtration rate.

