**Table 9.29 Laboratory parameters. Urinalysis. Absolute values. Safety population. N = xx**

Similar

**Parameters to be presented:** Color, Clarity, Specific gravity, pH, Protein, Glucose, Bilirubin, Urobilinogen, Ketone bodies, Nitrites, Hemoglobin.

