**Table 9.30 Laboratory parameters. Microscopic urine examination.**  
**Absolute values. Safety population. N = xx**  
**Similar**

**Parameters to be presented:** Epithelium, Erythrocytes, Leukocytes, Casts, Bacteria, Salts.

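### SAP 7.3.2 asks for means and numeric changes of qualitative urine items, and its liver-test outputs show neither elevation against the local limit nor within-patient category shift (minor)

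*SAP*

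**What the plan says.** SAP 7.3.2 plans two parallel summaries: "Laboratory data will be summarized by treatment group as clinical relevance (normal/abnormal, without clinical relevance/ abnormal, with clinical relevance) and as continuous data (absolute values". It then adds, without exception, that "All laboratory data and changes from baseline will be described as continuous variables at each visit". For the between-group comparison it narrows the data: "Only clinically significant deviations (CS) will be taken into account". That comparison is a permutation test on each set of parameters.

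The shells follow the text.

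- **Categorical.** Tables 9.19, 9.21, 9.23 and 9.25 give counts of no data, deviation that is not clinically significant (CNS), clinically significant deviation (CS) and normal, by arm, at Day 1 and at Day 8. Tables 9.20, 9.22, 9.24 and 9.26 repeat the CS counts with one p-value per visit.
- **Continuous.** Table 9.27 gives N, mean (SD), median and range for Day 1, Day 8 and the change. Tables 9.28 to 9.30 are declared similar to it. Table 9.28 covers "Total protein, Albumin, Total cholesterol, Total bilirubin, Conjugated bilirubin, ALT, AST, Serum creatinine, Glomerular filtration rate"; Table 9.29 covers "Color, Clarity, Specific gravity, pH, Protein, Glucose, Bilirubin, Urobilinogen, Ketone bodies, Nitrites, Hemoglobin"; Table 9.30 covers "Epithelium, Erythrocytes, Leukocytes, Casts, Bacteria, Salts".

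In the protocol, section 6.11 uses local laboratories and says that "all local laboratories will provide the required certificates and laboratory reference values". The investigator assesses every abnormal value. Section 6.12.11 turns new or worsened clinically significant abnormalities into adverse events. Section 9.8 asks for laboratory tables with change from baseline. Section 3.3.4 lists among the known side effects of the test drug "Hepatobiliary disorders: Cholestatic hepatitis", and promises particular attention to events in essential organs, including through laboratory results.

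**The concern.** Two things look wrong.

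First, colour, clarity and nitrites are labels. Their mean and their difference from Day 1 either do not exist or depend only on how the labels are coded. A programmer who follows SAP 7.3.2 must print meaningless numbers or depart from the plan.

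Second, the liver tests bear on a listed side effect, yet none of their outputs shows how large an elevation is on a scale that means the same at all 8 sites. The averages pool raw values from laboratories with their own reference values. The categories carry no size, and CS is separated from CNS by an investigator who knows the arm.

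What is at stake is the clarity of the safety description. The primary comparison is not involved.

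**Working it through.** The point does not rest on a stated figure. The only plan figure used is 92 per arm, as the expected safety denominator. It reproduces from the formula in Protocol 9.2: (1.96 + 0.84)² × (0.7 × 0.3 + 0.7 × 0.3) / 0.20² = 7.84 × 0.42 / 0.04 = 82.32, and 82.32 / 0.9 = 91.5, rounded up to 92.

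**1. Which parameters have which format.** Tables 9.27 to 9.30 list 16 haematology + 9 biochemistry + 11 urinalysis + 6 microscopy = 42 parameters. The same 42 are covered by the categorical Tables 9.19, 9.21, 9.23 and 9.25. So every parameter has both formats, and none is analysed only as a raw continuous value.

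**2. Where the continuous rule fails.** Of the 11 items in Table 9.29, at least colour, clarity and nitrites (3 of 11) have no numeric scale. Of the 6 in Table 9.30, bacteria, casts and salts (3 of 6) have none if the laboratory reports them as graded or present/absent. The documents do not state the reporting format. For the same reason it cannot be settled whether urine protein or bilirubin, for example, is numeric.

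**3. Whether the categorical tables supply the change.** They do not. They give a count at Day 1 and a count at Day 8. Suppose that *a* patients are abnormal at Day 1 and *b* at Day 8, among *n* with both results. The number newly abnormal is *b* minus the number abnormal at both visits. It can lie anywhere from max(0, *b* − *a*) to min(*b*, *n* − *a*). When *a* = *b*, and 2*a* is no more than *n*, that is anywhere from none to all *b*. This matters because Protocol 4.4 and 6.11 randomise before laboratory results are available, so patients with abnormal Day 1 values can be in the tables. For the qualitative urine items, the only output that answers the change requirement of Protocol 9.8 is therefore the invalid numeric one.

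**4. Liver tests: local limits.** The documents give no upper limits of normal. If local ALT limits ranged over 31 to 55 U/L (an assumption), a raw ALT of 90 U/L would be 90/31 = 2.9 times the limit at one site and 90/55 = 1.6 times at another. Table 9.28 treats the two as equal.

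**5. Liver tests: what the pooled table shows.** Suppose two of 92 patients rise from 25 to 200 U/L (assumed values). The arm mean moves by 2 × (200 − 25) / 92 = 3.8 U/L, which is easy to overlook. But the same table prints the range: the maximum would be at least 200 and the largest change at least 175. The rise would be visible. What would not be visible is the local limit it should be read against, or whether bilirubin rose in the same patient.

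**6. Liver tests: the comparison.** Table 9.22 gives one p-value per visit for all nine biochemistry parameters, from CS deviations only. It is not specific to the liver.

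**The case against.** A reader might infer that the listed hepatic harm has no analysis on a valid scale, or that only unblinded significance judgements and raw listings could reveal it. The documents do not support either reading.

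- The liver tests have normal/CNS/CS counts by arm and visit in Table 9.21, and CS counts in Table 9.22.
- The line between normal and abnormal is most naturally read as the local reference range, although the documents do not say so outright. Only the line between CNS and CS is plainly a judgement.
- ALT, AST and serum bilirubin are truly continuous, so describing them as such is no scale error, and Table 9.28 prints range and change.
- New or worsened clinically significant abnormalities reach the adverse-event tables, as clinical hepatitis itself would. SAP 7.3.7 adds a listing of patients with abnormal values.

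All of this stands and limits the point.

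It can also be said that a footnote to SAP section 9 lets report tables differ from the templates, that valid counts for the urine items already exist, and that nothing in the documents requires a table in multiples of the upper limit. The first does not rescue the rule: the footnote keeps the meaning and information of the templates, and the instruction is in the body of 7.3.2. The second is true visit by visit but not for change. The third is fair: the liver table is an improvement, not the repair of a breach. It is justified because the side effect is listed, the promise of attention is in the protocol, and the laboratories supply their reference values.

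**Conclusion.** The point holds in a limited form and is minor.

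- **Urine items.** The rule in SAP 7.3.2 is wrong for at least 3 of 11 urinalysis items. It is also wrong for 3 of 6 microscopy items if those are graded or present/absent. Their category counts are valid at each visit but do not show change.
- **Liver tests.** They are analysed, in several ways. What is missing is the size of an elevation against the local limit, a within-patient shift between categories, and a count of patients with transaminase and bilirubin raised together. The conclusion that hepatic harm goes unanalysed would be false.

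The ALT limits of 31 to 55 U/L and the two-patient example are assumptions that only illustrate the mechanism. The findings on the shells come from the documents alone. Nothing here affects the primary non-inferiority conclusion.

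**What to change.** Change SAP 7.3.2 and the related shells before database lock.

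1. Limit the continuous summary to measured quantities. In Tables 9.29 and 9.30, replace the numeric change for qualitative or graded items by counts of patients by Day 1 category and Day 8 category (a shift table), by arm.
2. For ALT, AST, total and conjugated bilirubin, add one descriptive table by arm of Day 8 or early-discontinuation values as multiples of the local upper limit. Use a single set of bands fixed before lock, show the Day 1 category alongside, and count patients with transaminase and bilirubin raised together. The bands serve tabulation only and imply no rule for managing patients.

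No new visits or samples are needed, and the extra programming is slight. The real condition is that the local reference limits be in the analysis dataset. Protocol 6.11 has the laboratories supply them, but the documents do not confirm that they are captured, and the listing described in SAP 7.3.7 has units and a significance flag but no limits. If they must be entered, the task is small: with one laboratory per site and one limit per test (both assumed), 4 tests × 8 sites = 32 values, and more if limits differ by sex or change over time.

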4.4 Patient Withdrawal After Randomization

The randomization procedure will be performed before laboratory test results are available. In case of significant abnormalities that in the Investigator's opinion interfere with the patient's participation in the study, the patient should be withdrawn from the study.

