6.12.11 Clinically Significant Laboratory Abnormalities

Any clinically significant abnormalities of laboratory parameters or results of the instrumental methods of examination noted at screening shall be registered in the patient's medical history. After screening, new or worsened clinically significant abnormalities shall be reported as adverse events in source documents and CRF.

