7.5 Early Termination Visit

In case of early withdrawal from the study after Visit 1 (Randomization) and before Visit 3 (Day 8) the patient should be invited to the study site for early termination visit (ETV). Investigator should make all reasonable efforts to perform all the required assessments at the ETV. Early termination visit should occur not later than on Day 3 after the last dose of the study drug.

ETV should include all procedures of Visit 3, (Day 8). If ETV cannot be performed in full volume, the Investigator should agree his/her actions with the Medical Monitor.

At ETV the patient should return to the site all used and unused packages of the study drug. The patient will be given recommendations for further treatment within standard ARVI treatment options.

If possible, the Investigator should discuss patient withdrawal with Medical Monitor in advance. Otherwise, the Investigator should contact the Medical Monitor within 24 hours after the early termination visit.

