9.8 Safety Analysis

All patients who receive at least one dose of the study drug will be included into the safety population.

The number and percentage of the patients with AE and SAE for every treatment group (along with the total numbers) will be summarized in tables by system organ class and preferred term, relationship to the study drug and severity; the laboratory results will be summarized in tables with change from baseline. The vital signs, laboratory and spirometry results will be summarized by means of descriptive statistics.

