#### **7.3.1 Adverse Events**

Adverse Events will be summarized by treatment groups. Relation of AE to the therapy will be defined by AE onset date and period start date for the patient. All AEs will be coded with MEDDRA dictionary. AEs will be summarized by SOC (System Organ Class) and PT (Preferred Terms).

Adverse Events (if any) started before the first dose of the study drug(s) will be presented in the separate table.

AE frequencies will be compared between treatment groups. For such comparisons MedDRA Preferred Terms (PT) will be used. Treatment groups will be compared by set of frequencies of PT terms using permutation tests. One p-value will be provided ( $H_0$ : treatment groups are equal in set of AE frequencies).

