**Table 9.17 Urine pregnancy test (females only). Safety population. N = xx**

	Levopront® (T) n (%) N = XX	Libexin® (C) n (%) N = XX
Screening (Day 1)		
Positive	xx (xx.x%)	xx (xx.x%)
Negative	xx (xx.x%)	xx (xx.x%)
No data	xx (xx.x%)	xx (xx.x%)
Day 8/ED		
Positive	xx (xx.x%)	xx (xx.x%)
Negative	xx (xx.x%)	xx (xx.x%)
No data	xx (xx.x%)	xx (xx.x%)

**Table 9.18 Concomitant medication. Safety population.  
During the study. N = xx**

ATC code Drug	Levopront® (T) n (%) N = XX	Libexin® (C) n (%) N = XX
Group		
Total	xx (xx.x%)	xx (xx.x%)
DRUG (ATC)	xx (xx.x%)	xx (xx.x%)
...		

**Table 9.19 Laboratory parameters. Hematology. Deviation from normal values.  
Safety population. N = xx**

Parameter	Day 1		Day 8/ET	
	Levopront®	Libexin®	Levopront®	Libexin®
Hemoglobin				
No data	xx (xx.x%)	xx (xx.x%)	xx (xx.x%)	xx (xx.x%)
CNS deviation	xx (xx.x%)	xx (xx.x%)	xx (xx.x%)	xx (xx.x%)
CS deviation	xx (xx.x%)	xx (xx.x%)	xx (xx.x%)	xx (xx.x%)
Normal	xx (xx.x%)	xx (xx.x%)	xx (xx.x%)	xx (xx.x%)
Hematocrit				
No data	xx (xx.x%)	xx (xx.x%)	xx (xx.x%)	xx (xx.x%)
CNS deviation	xx (xx.x%)	xx (xx.x%)	xx (xx.x%)	xx (xx.x%)
CS deviation	xx (xx.x%)	xx (xx.x%)	xx (xx.x%)	xx (xx.x%)
Normal	xx (xx.x%)	xx (xx.x%)	xx (xx.x%)	xx (xx.x%)
...				

**Parameters to be presented:** Hemoglobin, Hematocrit, RBC, WBC, Neutrophils (abs), Lymphocytes (abs), Monocytes (abs), Eosinophils (abs), Basophils (abs), Platelets, ESR, Neutrophils (%), Lymphocytes (%), Monocytes (%), Eosinophils (%), Basophils (%).

**Table 9.20 Laboratory parameters. Hematology. CS deviations only. Safety  
population. N = xx**

Parameter	Day 1		Day 8/ET	
	Levopront®	Libexin®	Levopront®	Libexin®
Hemoglobin				
CS deviation	xx (xx.x%)	xx (xx.x%)	xx (xx.x%)	xx (xx.x%)
Hematocrit				
CS deviation	xx (xx.x%)	xx (xx.x%)	xx (xx.x%)	xx (xx.x%)
...				
p-value 		0.xxx		0.xxx

**Table 9.21 Laboratory parameters. Biochemistry. Deviation from normal  
values. Safety population. N = xx**

Parameter	Day 1		Day 8/ET	
	Levopront®	Libexin®	Levopront®	Libexin®
Total protein				
No data	xx (xx.x%)	xx (xx.x%)	xx (xx.x%)	xx (xx.x%)

 For the set of parameters at visit

Parameter	Day 1		Day 8\ET	
	Levopront®	Libexin®	Levopront®	Libexin®
CNS deviation	xx (xx.x%)	xx (xx.x%)	xx (xx.x%)	xx (xx.x%)
CS deviation	xx (xx.x%)	xx (xx.x%)	xx (xx.x%)	xx (xx.x%)
Normal	xx (xx.x%)	xx (xx.x%)	xx (xx.x%)	xx (xx.x%)
Albumin				

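### The between-arm laboratory test counts clinically significant deviations already present on Day 1, which lowers its sensitivity to drug-emergent ones

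*SAP*

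**What the plan says.** SAP 7.3.2 compares the arms separately for the hematology, biochemistry, urinalysis and urine microscopy sets by permutation test. On what is counted it says: "Only clinically significant deviations (CS) will be taken into account". The shells for this test are Tables 9.20, 9.22, 9.24 and 9.26. Each has one pair of columns for Day 1 and one for Day 8/ET, with a p-value under each pair. The footnote to the p-value in Table 9.20 reads "For the set of parameters at visit". There is no shift table.

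The same SAP section adds, without a test: "All laboratory data and changes from baseline will be described as continuous variables at each visit". Protocol 9.8 likewise says that "the laboratory results will be summarized in tables with change from baseline".

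Protocol 6.12.11 assigns clinically significant findings at screening to medical history and then says: "After screening, new or worsened clinically significant abnormalities shall be reported as adverse events in source documents and CRF". Protocol 4.4 explains how such findings can occur in randomised patients: "The randomization procedure will be performed before laboratory test results are available".

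On early termination, protocol 7.5 says "ETV should include all procedures of Visit 3, (Day 8"), which covers blood and urine sampling. SAP Tables 9.19 to 9.26 head the last visit *Day 8/ET*, whereas Table 9.27 heads it *Day 8/ET or ED*. The abbreviations under SAP Table 2.1 define ET as end of treatment and ED as early discontinuation.

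**The concern.** A safety comparison after treatment should contrast what happened after treatment began. Here a patient with the same clinically significant value on Day 1 and Day 8 counts as a Day 8 finding, although the protocol treats that value as medical history. Such patients are plausible. They enter with an acute infection and are dosed before their laboratory results are known. They leave only if the investigator judges that the abnormality interferes with participation (protocol 4.4 and 6.11). Anyone who took a dose stays in the safety population (SAP 5.3), which SAP 7.3 analyses.

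Carried-over cases fall on both arms alike. They add variance and pull the risk ratio towards 1, so a real excess is less likely to show. The danger is false reassurance: a large p-value in these tables could be read as no laboratory signal when much of what was counted predates treatment.

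**Working it through.** **Which comparisons take account of Day 1**

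| Laboratory output | Tested between arms? | Accounts for Day 1? |
|---|---|---|
| Tables 9.20, 9.22, 9.24, 9.26 (clinically significant deviations) | Yes, one p-value per set and visit | No |
| Tables 9.27 to 9.30 (absolute values) | No | Yes, change column in 9.27; the others are marked similar |
| AE tables, through protocol 6.12.11 | Yes, one p-value over all preferred terms, plus Fisher rows in Table 9.33 | Yes, new or worsened only |

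The test in SAP 7.3.2 is thus a count at each visit with no conditioning on baseline.

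**The plan's own figure.** The documents state no figure for the laboratory comparison. The arm size used below does reproduce. With z-values 1.96 and 0.84, 70% response in both arms and a margin of 20% (protocol 9.2), n = (1.96 + 0.84)² × (0.7 × 0.3 + 0.7 × 0.3) / 0.2² = 7.84 × 0.42 / 0.04 = 82.3. Allowing 10% early discontinuation, 82.3 / 0.9 = 91.5, so 92 per arm.

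**Illustration of the dilution.** All rates here are assumptions. Let b be the proportion in each arm with a Day 1 deviation that persists, and e the emergent rate among the rest.

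- Unfiltered Day 8 proportion: b + (1 − b)e
- Filtered proportion (new only): (1 − b)e

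Example with b = 5% and e = 10% versus 1%:

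- Unfiltered: 0.05 + 0.95 × 0.10 = 14.5% versus 0.05 + 0.95 × 0.01 = 5.95%, risk ratio 2.4
- Filtered: 9.5% versus 0.95%, risk ratio 10

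Exact power of a two-sided Fisher test at 0.05 with 92 per arm:

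| Emergent rates | Carry-over b | Unfiltered risk ratio | Power unfiltered | Power filtered |
|---|---|---|---|---|
| 10% vs 1% | 0% | 10.0 | 71.5% | 71.5% |
| | 2% | 4.0 | 54.8% | 70.1% |
| | 5% | 2.4 | 39.2% | 67.9% |
| | 10% | 1.7 | 27.0% | 64.0% |
| 15% vs 3% | 0% | 5.0 | 78.3% | 78.3% |
| | 2% | 3.4 | 67.0% | 77.2% |
| | 5% | 2.5 | 54.9% | 75.5% |
| | 10% | 1.9 | 41.0% | 72.4% |

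The risk difference, (1 − b) times the difference in e, hardly moves: 9.0 percentage points at b = 0 and 8.1 at b = 10% in the first scenario. Most of the loss therefore comes from added variance.

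Single splits show how much depends on the counts chosen. Six new cases against none gives p = 0.029, and adding three carried-over cases per arm (9 vs 3) gives 0.133. Ten against none plus three per arm (13 vs 3) still gives 0.016.

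The Fisher test on one yes/no variable stands in for the planned multi-parameter permutation test. The direction carries over, but the percentages do not.

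**The case against.** The strongest reply is that emergent laboratory abnormalities are already compared elsewhere. Under protocol 6.12.11 every new or worsened clinically significant abnormality is an adverse event. It then enters the AE tables, the AE permutation test and the Fisher-tested summary in Table 9.33, across the whole safety population including early discontinuers. Events from before treatment are kept apart: "Adverse Events (if any) started before the first dose of the study drug(s) will be presented in the separate table". Change from baseline is tabulated, the Day 1 counts stand next to the Day 8 counts, and SAP 7.3.7 plans a listing of patients with abnormal values. All of this stands. A reader might infer that drug-emergent abnormalities would be missed; the documents do not support that. What the reply leaves untouched is the laboratory test itself. The AE test gives one p-value over all preferred terms, and the continuous changes are not tested.

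A reader might also infer from the *Day 8/ET* heading that early-termination samples are excluded from the tested tables. At the protocol's 10% ceiling that would be about 9 patients per arm (0.10 × 92 = 9.2). The documents point to inconsistent labelling instead. The schedule has a single column for ET or ED. Table 9.17 is headed *Day 8/ED*, which read literally would drop the patients who completed treatment. A footnote to SAP section 9 allows the final tables to differ from the templates as long as their content is kept. No SAP text excludes these samples.

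Finally, the SAP sets no alpha for safety, so no planned decision turns on this p-value. That limits the consequence but does not make the count the right one.

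**Conclusion.** The point holds as a loss of sensitivity in one safety test. The test in SAP 7.3.2 mixes Day 1 abnormalities with emergent ones, contrary to the distinction in protocol 6.12.11. Any persisting Day 1 case dilutes the Day 8 comparison.

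It does not bias one arm against the other, since randomisation balances such cases in expectation. The size cannot be fixed from the documents, which give neither the rate of clinically significant abnormalities nor how often they persist. The power figures above rest on assumed rates and a substitute test. They show direction only.

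The heading in Tables 9.19 to 9.26 needs clarifying but is not evidence of an exclusion. The two matters are linked: patients withdrawn because of their Day 1 results are due an early termination visit with the same sampling. Including that visit without the new-or-worsened restriction could therefore bring in more carried-over cases.

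**What to change.** 1. In SAP 7.3.2 and Tables 9.20, 9.22, 9.24 and 9.26, base the between-arm comparison on patients with a clinically significant deviation that is new or worsened since Day 1, as in protocol 6.12.11. State how worsening is identified when a parameter is flagged on both days, for example by the investigator's AE report, and how a missing Day 1 value is handled.
2. Keep the Day 1 counts of clinically significant deviations as descriptive columns.
3. Head the last visit in Tables 9.19 to 9.26 *Day 8/ET or ED*, as in Table 9.27, so that early-termination samples are clearly included.

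The cost is a few lines of SAP text and edits to table shells before database lock. The Day 1, Day 8 and early-termination results and the AE reports are already collected under the protocol.
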